Letter of Amendment Signature Page

I will conduct this study in accordance with the provisions of this protocol and all applicable protocol-related documents. I agree to conduct this study in compliance with United States (US) Health and Human Service regulations (45 CFR 46); applicable US Food and Drug Administration regulations; standards of the International Conference on Harmonization Guideline for Good Clinical Practice (E6); Institutional Review Board/Ethics Committee determinations; all applicable in-country, state, and local laws and regulations; and other applicable requirements (e.g., US National Institutes of Health, Division of AIDS) and institutional policies.

Signature of Investigator of Record

Date

Name of Investigator of Record
(printed)

Summary of Modifications and Rationale

The following modifications are included in this LoA:

1. Sections 6.5, 6.7, and 9.2 are modified to clarify the pharmacokinetic (PK) criteria for early study drug discontinuation for participants with $AUC_{0-12hr} \geq 63 \mu Mxhr$.
2. Section 7.2 is updated to clarify that confirmed Grade 3 and 4 adverse events are required to be reported as expedited adverse events.

Implementation

Detailed modifications of the protocol text included in this LoA are listed below. Additions to the text are indicated in **bold**; deletions are indicated by ~~striketrough~~.

1. Pharmacokinetic criteria for early study drug discontinuation

a. Section 6.5, Pharmacokinetic Endpoint, second paragraph:

~~RAL will be stopped in any individual that has an $AUC_{0-12hr} \geq 63 \mu Mxhr$, per Section 9.0. Per~~ **Section 9.0, if any individual has an $AUC_{0-12hr} \geq 63 \mu Mxhr$, the Protocol Team will review all available clinical, safety, PK, immunologic, and virologic data for the participant and determine if discontinuation of RAL is indicated. For participants that permanently discontinue RAL, evaluable PK and safety data will be used in the assessment of the dose for that cohort.**

b. Section 6.7, Criteria for Early Treatment Discontinuation, fifth bullet:

- Participant has an $AUC_{0-12hr} \geq 63 \mu Mxhr$, **and the protocol team determines that RAL should be permanently discontinued**, per Section 9.0.

c. Section 9.2, Study Design, Modeling and Data Analysis, Pharmacokinetic Guidelines, sixth paragraph:

If any individual has an $AUC_{0-12hr} \geq 63 \mu Mxhr$ **, **the Protocol Team will review all available clinical, safety, PK, immunologic, and virologic data for the participant and determine if discontinuation of RAL is indicated** ~~participant will stop taking RAL. However, their~~ **For participants that permanently discontinue RAL, evaluable PK and safety data will be used in the assessment of the dose for that cohort.**

2. Expedited Adverse Event Reporting Requirements

Section 7.2, Reporting Requirements for this Study, second bullet:

- Other medically significant events for which expedited reporting is required include all cancers and pregnancies, fetal losses, IRIS events that qualify as serious adverse events, Hy's Law liver toxicities, and all **confirmed** Grade 3 and 4 toxicities.

This is IMPAACT P1101 SAP Version 1.0 with names of authors, names of publication, writing team members, and analysis timeline redacted.

Pharmacokinetic Statistical Analysis Plan

Version 1.0

IMPAACT P1101

Phase I/II dose-finding, Safety, Tolerance and Pharmacokinetics Study of a Raltegravir-Containing Antiretroviral Therapy (ART) Regimen in HIV-infected and TB Co-infected Infants and Children

ClinicalTrials.gov Identifier: NCT01751568

October 5, 2020

TABLE OF CONTENTS

1. Introduction	3
2. PK-Related Study Background	3
3. Dose-Finding Approach	3
4. Primary Pharmacokinetic Study Objectives	4
5. Non-Compartmental Pharmacokinetic Analyses	4
5.1. Below the Level of Quantitation	5
5.2. Terminal Slope Estimation	5
5.3. AUC Values	5
6. Summary Statistics	5
7. Presentation of Data	6

1. Introduction

This Pharmacokinetic Statistical Analysis Plan (PK SAP) is complementary to the IMPAACT P1101 Primary SAP (version 2.0) and the IMPAACT P1101 PK Data Management Plan (version 2.0). This document describes the non-compartmental pharmacokinetic (PK) analysis to be performed by the IMPAACT P1101 protocol pharmacologist at the end of study on the completed study dataset and included in study abstracts and manuscripts.

2. PK-Related Study Background

IMPAACT P1101 is a Phase I/II dose-finding, safety, tolerance and pharmacokinetics study of a raltegravir (RAL)-containing antiretroviral therapy (ART) regimen in HIV-infected and TB co-infected infants and children. There is an urgent need for better tolerated, potent, simple agents (i.e. simple dosing, administration and storage) to be included in first line ART regimens to widen the treatment options for children and infants co-infected with TB and HIV. Based on data from prior studies of drug interactions of RIF and RAL in adults, doubling the dose of RAL to 12 mg/kg/dose (maximum 800 mg/dose) is an appropriate starting point for this study. The UGT1A1 metabolic pathway is fully mature after the first 3 months of life; therefore, co-administration of RAL and RIF is expected to lead to significant reductions in RAL concentrations in children. As pediatric RAL dosing regimens have been shown to achieve PK parameters comparable to those in adults, doubling the RAL dose for children when given with RIF will likely yield similar improvements in PK parameters. Participants will be enrolled into the study into the following cohorts:

- Cohort I: ≥ 2 to < 6 years of age on TB treatment (n = 12 minimum)
- Cohort II: ≥ 6 to < 12 years of age on TB treatment (n = 12 minimum)
- Cohort III: ≥ 4 weeks to < 2 years of age on TB treatment (n = 12 minimum)

Cohorts I, II, III will enroll simultaneously. Each age cohort will start with a mini-cohort of six participants, followed by six additional participants to make up a full cohort.

3. Dose-Finding Approach

HIV-infected and TB co-infected children ≥ 4 weeks to < 12 years of age taking RIF-based TB therapy and who are eligible for antiretroviral (ARV) treatment as defined by local or WHO guidelines. An initial dose of RAL will be given at 12 mg/kg (up to a maximum of 800 mg) twice daily for chewable formulation, with two NRTIs. Following the intensive PK study for RAL (5 to 8 days after the start of RAL therapy), a fourth ARV drug will be added to the regimen. The four-drug ARV regimen will be continued until TB treatment is completed. Each child will be followed up to assess safety, clinical, immunological and virological parameters, from the time that RAL is started on a TB containing regimen until 3 months after stopping RAL while standard of care treatment continues.

Each age cohort will start with a mini-cohort of six participants to assure that preliminary PK and safety criteria are met at that dose. Data from each age cohort will be reviewed independently and, if the mini-cohort data meets established metrics an additional 6 participants per age cohort will be enrolled (full cohort), and evaluated for safety and PK. If the mini-cohort (n = 6) at a RAL dose of 12 mg/kg achieves 1) a geometric mean RAL AUC_{0-12hr} of approximately 14 to 45 μMxhr and 2) an approximate GM C_{12h} ≥ 75nM, and meets safety criteria, then 6 additional participants will be enrolled at this dose. The data from these participants will be combined with the previous 6 for evaluation of this dose using the same criteria.

If the initial mini-cohort of n = 6 fails either the safety or the PK guidelines in this initial test, then the dose will be adjusted in the appropriate direction, unless dose reduction is likely to result in inadequate PK values. An initial evaluation of the new dose level will be made on the basis of data from the first six new participants treated at this dose. If the first six participants of a cohort meet both sets of guidelines, then six additional participants will be accrued to this cohort. The additional six participants will be evaluated on both safety and PK; if the full cohort of n = 12 passes both safety and PK criteria, then the dose on which they have been treated will become the selected dose.

Note: Please see Section 8.5.1 of the protocol V3.0 for details regarding Safety Guidelines.

4. Primary Pharmacokinetic Study Objectives

To determine the pharmacokinetics and appropriate dose of RAL when administered with a RIF-containing anti-TB therapy in HIV/TB co-infected infants and children that generates PK parameters generally comparable to those seen in HIV-infected infants and children in the absence of RIF.

5. Non-Compartmental Pharmacokinetic Analyses

PK sampling was collected at pre-dose (0), 0.5, 1, 2, 3, 4, 6, 8, and 12 hours post dosing. A single 0.5 mL sample of whole blood was collected at each time point. Standard non-compartmental methods for PK parameter derivation will be performed using Phoenix WinNonlin 8.1 (or current, Certara USA, Inc.). Where possible, the following PK parameters will be determined from RAL plasma concentration-time data:

Parameter	Definition
C _{max}	Observed maximum plasma concentration
T _{max}	Time of maximum plasma concentration
AUC ₍₀₋₁₂₎	Area under the concentration-time curve from time zero to the end of the dosing interval at 12 hours at steady-state

CL_{ss}/F	Apparent oral clearance at steady-state
V_z/F	Apparent distribution volume at steady-state
λ_z	Terminal elimination rate constant
$t_{1/2}$	Terminal half-life calculated as $\ln(2)/\lambda_z$
C_{12h}	Concentration at the end of the dose interval at 12 hours

Additional PK parameters may be determined where appropriate. Pharmacokinetic analysis will be carried out using actual sampling times provided by the UAB PSL.

5.1. Below the Level of Quantitation

RAL concentration values that are below the level of quantification (LLOQ), < 10 ng/mL, will be set to ½ the LLOQ. If an entire concentration-time profile is LLOQ, the profile will be excluded from the PK analysis. If a pre-dose concentration is below the limit of assay detection, this value is set to ½ the LLOQ. Any embedded BLQ value (BLQ value occurring between two quantifiable concentrations) in a profile will be set to missing for the purposes of PK analysis.

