5.2. Terminal Slope Estimation

The default settings for the analysis software will only estimate an elimination rate constant when the PK profile has three or more declining concentrations after the peak concentration in a non-compartmental analysis. In the case of only two terminal concentrations can be chosen for $t_{1/2}$ determination, these points will be chosen by pharmacokineticist.

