5.3. AUC Values

AUC is calculated by the linear trapezoidal rule. Since this study is evaluating RAL PK at steady-state, the only important AUC parameter is the 12 hour result, AUC_{0-12h} .

6. Summary Statistics

All individual concentrations and all pharmacokinetic parameters will be summarized using descriptive statistics. These will include the n, mean, standard deviation, CV%, median, range and geometric mean. For dissemination, selected descriptive statistics on evaluable participants will be used as appropriate for the data distribution. PK parameters will be summarized by cohort.

7. Presentation of Data

Concentration time profiles (for individual infants, strata, and/or cohorts) will be presented graphically. For summary statistics and median/mean plots by sampling time, the nominal PK sampling time will be used. For individual subject plots by time, the actual PK sampling time will be used. RAL concentrations and PK parameters will be listed out separately for any participant not included in the dose-finding population. Additional tables, listings or figures may be prepared upon request.

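### A below-LLOQ value at the end of a profile, imputed as 5 ng/mL, is not kept out of the terminal-slope fit, so lambda_z, half-life and Vz/F can rest on an arbitrary constant in the few profiles affected (minor)

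*SAP*

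**What the plan says.** SAP Section 5.1 gives a general rule: "RAL concentration values that are below the level of quantification (LLOQ), < 10 ng/mL, will be set to ½ the LLOQ". It adds three special cases. A profile wholly below the LLOQ is excluded, a pre-dose value below the limit becomes half the LLOQ, and "Any embedded BLQ value (BLQ value occurring between two quantifiable concentrations) in a profile will be set to missing".

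Section 5.2 leaves lambda_z to the software default, which needs "three or more declining concentrations after the peak concentration". If only two terminal values can be used, "these points will be chosen by pharmacokineticist".

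Section 5 gives the schedule ("PK sampling was collected at pre-dose (0), 0.5, 1, 2, 3, 4, 6, 8, and 12 hours post dosing") and lists lambda_z, half-life as ln(2)/lambda_z, and Vz/F among the outputs: "Where possible, the following PK parameters will be determined from RAL plasma concentration-time data". Section 6 reports them: "All individual concentrations and all pharmacokinetic parameters will be summarized using descriptive statistics", and "PK parameters will be summarized by cohort".

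Section 3 bases the PK dose criteria on geometric mean AUC0-12 (about 14 to 45 μM×hr) and geometric mean C12h (at least about 75 nM). Section 5.3 computes AUC0-12 by the linear trapezoidal rule. Section 1 says that this SAP complements a Primary SAP and a PK Data Management Plan, neither of which was available for this review.

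**The concern.** A below-LLOQ value in the last sample has no quantifiable value after it. It is therefore not embedded, and the general rule makes it 5 ng/mL. It lies below any quantifiable value before it, so it counts as declining and can even supply the third point that the default requires. At 12 h it is also the point with the most leverage on the slope. Section 5.2 describes manual choice of points only for the two-point case and does not bar an imputed value there.

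The SAP thus keeps imputed numbers out in the middle of a profile but not at its end, where they affect the slope most. Two competent analysts could report different half-lives for the same child. At stake are the individual values, ranges and cohort summaries of lambda_z, half-life and Vz/F in abstracts and manuscripts.

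**Working it through.** The plan gives no half-life figure to reproduce, so the check follows the stated rules through.

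**Inputs from the SAP.** LLOQ 10 ng/mL, imputed value 5 ng/mL, samples at 4, 6, 8 and 12 h, 12 participants per full cohort, C12h criterion 75 nM, AUC0-12 criterion 14 to 45 μM×hr.

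**Assumptions not in the documents.** Molar mass 444 g/mol, so 75 nM = 75 × 0.444 = 33.3 ng/mL. Lognormal C12h with CV 50 to 150%. Mono-exponential decline with rate k = ln(2)/half-life, except in step 5.

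**1. One imputed value at 12 h.** In a log-linear least-squares fit, replacing the true C12 by 5 gives

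lambda_est = k + w × ln(C12/5), with w = (12 − mean t)/Sxx.

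For 6/8/12 h, w = 3.333/18.67 = 0.179. For 4/6/8/12 h, w = 4.5/35 = 0.129.

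Example: true half-life 2 h (k = 0.3466), concentrations 128, 64, 32 and 8 ng/mL at 4, 6, 8 and 12 h, with ln(8/5) = 0.470.
- 6/8/12 h: 0.3466 + 0.179 × 0.470 = 0.4305, half-life 1.61 h.
- 4/6/8/12 h: 0.3466 + 0.129 × 0.470 = 0.4070, half-life 1.70 h.
- Quantifiable 4/6/8 h only: 2.00 h.

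**2. Direction.** The sign is that of ln(C12/5). For a true half-life of 2 h and the 6/8/12 h fit:

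| True C12 (ng/mL) | Estimated half-life (h) | Error |
|---|---|---|
| 9 | 1.54 | −23% |
| 7.5 | 1.65 | −17% |
| 6 | 1.83 | −9% |
| 5 | 2.00 | 0% |
| 4 | 2.26 | +13% |
| 3 | 2.71 | +36% |

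Vz/F moves by the same ratio as half-life, because it is CL/F divided by lambda_z.

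If 8 h and 12 h are both below the LLOQ (true 16, 8 and 2 ng/mL at 6, 8 and 12 h, fitted as 16, 5 and 5), the estimate is 4.17 h for a true 2 h. The two imputed values tie, and the SAP does not say whether a tie counts as declining.

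**3. Frequency.** P(C12 < 10) = Φ(ln(10/GM)/σ), with σ = √ln(1 + CV²).

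| GM C12h | CV | P(ends below LLOQ) | Expected of 12 | P(at least one of 12) | Of these, true C12 < 5 |
|---|---|---|---|---|---|
| 75 nM | 50% | 0.5% | 0.1 | 6% | 0.5% |
| 75 nM | 100% | 7.4% | 0.9 | 60% | 15% |
| 75 nM | 150% | 13.4% | 1.6 | 82% | 30% |
| 150 nM | 50% | 0.003% | 0.0 | 0% | 0.1% |
| 150 nM | 100% | 1.1% | 0.1 | 13% | 8% |
| 150 nM | 150% | 4.0% | 0.5 | 39% | 21% |

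At 75 nM and a CV of 300%, 21.4% of profiles end below the LLOQ and 49% of those are below 5 ng/mL, so the sign is then close to even.

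**4. Cohort effect.** One affected child of 12 multiplies the cohort geometric mean half-life by ratio^(1/12). For the examples above: (1.61/2)^(1/12) − 1 = −1.8%, (1.70/2)^(1/12) − 1 = −1.3%, and with two imputed values (4.17/2)^(1/12) − 1 = +6.3%.

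**5. Consistency with the AUC criterion.** Under mono-exponential decline, extrapolating back to time 0 bounds AUC0-12 at C12 × (2^(12/half-life) − 1)/k.
- A child with C12 of 10 ng/mL or less has at most 10 × 15/0.2310/444 = 1.5 μM×hr at a 3 h half-life and 10 × 7/0.1733/444 = 0.9 at 4 h.
- A cohort with GM C12h of 75 to 150 nM has at most 4.9 to 9.7 μM×hr at 3 h and 3.0 to 6.1 at 4 h, below the lower limit of 14.
- At 2 h the cohort bound is 13.6 to 27.3 μM×hr, so a passing cohort is possible. The child in step 1 still has at most 8 × 63/0.3466/444 = 3.3, low but possible for one individual.

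If early decline is steeper, so that AUC meets the target, the tail is bi-exponential. Take phase half-lives of 1 and 3 h, AUC0-12 of 14 μM×hr and true C12 of 7.5 ng/mL. The estimated/true terminal half-life is 0.42 with the imputed value left out (4/6/8 h). With it kept, the ratio is 0.48 (6/8/12 h) or 0.46 (4/6/8/12 h).

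**The case against.** The strongest reply is that the matter is small and the analyst already has discretion. Section 5 says that parameters are derived where possible by standard methods, the pharmacokineticist picks the points for a two-point slope, and nothing obliges anyone to use an imputed value. The two companion documents may hold a rule. One affected child moves the cohort geometric mean by a few per cent, well inside sampling error: with an assumed between-child CV of 30 to 50%, the standard error of the log geometric mean in 12 children is about 8 to 14%. All of this stands, and it limits the severity. It does not close the gap, because the default fit as described admits the value and individual results and ranges are reported.

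The reply also limits what can be claimed. A reader might infer that half-life will usually be too short. That holds for a single value at 12 h with a moderate spread of C12h. The documents give no spread, the sign is near even at a CV of 300%, and it reverses with two trailing values.

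A reader might also quote larger errors at half-lives of 3 to 4 h (for example −24% at 3 h with true C12 of 7.5 ng/mL). Under mono-exponential decline those cases are inconsistent with a cohort that meets the AUC target, so they are not relied on here.

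Finally, a reader might infer that exclusion restores the true half-life. It does so only on a mono-exponential tail. On the bi-exponential tail above, both estimates fall far short and the one with exclusion is no closer.

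**Conclusion.** The gap is real and minor. As written, Sections 5.1 and 5.2 let an invented 5 ng/mL enter the lambda_z fit when a profile ends below the LLOQ, and half-life and Vz/F then depend on that constant. In the 2 h examples the individual error ranges from −23% to +36% with one imputed value, and is about +109% (4.17/2 − 1) with two. These figures assume a mono-exponential tail and a three-point fit. For cohorts at 75 to 150 nM with CV 50 to 150%, 0 to 1.6 profiles of 12 are expected to be affected; a cohort that misses the C12h criterion could have more.

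The documents do not support reading this as a threat to the dose decision: AUC0-12, as Section 5.3 describes it, and C12h do not use lambda_z. Nor do they support a fixed direction of bias. The conclusion also depends on the Primary SAP and PK Data Management Plan holding no rule for trailing values.

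**What to change.** Add to Section 5.2: *BLQ values set to 1/2 LLOQ are not used to estimate lambda_z, in the default fit or in a two-point slope; if fewer than two quantifiable post-peak concentrations remain, lambda_z, t1/2 and Vz/F are reported as not estimable, with the number of such participants.* Flag two-point estimates in listings and summaries. Leave the AUC0-12 and C12h rules unchanged. If either companion document already has this rule, cross-reference it instead.

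The cost is one sentence and one flag, with no new data. The fitted window becomes shorter. If only the 12 h value is below the LLOQ, three or more quantifiable post-peak values remain when Tmax is 3 h or earlier, two (6 and 8 h) when it is 4 h, and one when it is 6 h. Half-life is then lost only for Tmax of 6 h or later, or 4 h or later if 8 h is also below the LLOQ. Some of those children may be fast eliminators, so the count should stand beside the summary.

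A 6/8 h pair is imprecise. With an assumed 15% concentration error, the standard error of lambda_z is 0.1055, which is 15% of k at a 1 h half-life (0.1055/0.6931) and 30% at 2 h (0.1055/0.3466). That is the reason for the flag.

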5.2. Terminal Slope Estimation

The default settings for the analysis software will only estimate an elimination rate constant when the PK profile has three or more declining concentrations after the peak concentration in a non-compartmental analysis. In the case of only two terminal concentrations can be chosen for $t_{1/2}$ determination, these points will be chosen by pharmacokineticist.

5.3. AUC Values

AUC is calculated by the linear trapezoidal rule. Since this study is evaluating RAL PK at steady-state, the only important AUC parameter is the 12 hour result, AUC_{0-12h} .

6. Summary Statistics

All individual concentrations and all pharmacokinetic parameters will be summarized using descriptive statistics. These will include the n, mean, standard deviation, CV%, median, range and geometric mean. For dissemination, selected descriptive statistics on evaluable participants will be used as appropriate for the data distribution. PK parameters will be summarized by cohort.

7. Presentation of Data

Concentration time profiles (for individual infants, strata, and/or cohorts) will be presented graphically. For summary statistics and median/mean plots by sampling time, the nominal PK sampling time will be used. For individual subject plots by time, the actual PK sampling time will be used. RAL concentrations and PK parameters will be listed out separately for any participant not included in the dose-finding population. Additional tables, listings or figures may be prepared upon request.

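### Must Section 6 of the PK SAP name a confidence interval for the two dose-selecting geometric means, and a count of children at or above 63 μM·hr?

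*SAP*

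**What the plan says.** PK SAP Section 3 gives two PK criteria for a cohort: a GM AUC0-12 of roughly 14 to 45 μM·hr and "2) an approximate GM C_{12h} ≥ 75nM, and meets safety criteria". They are applied to a mini-cohort of 6 and again to the full cohort of 12. Section 4 states the aim as a dose that "generates PK parameters generally comparable to those seen in HIV-infected infants and children in the absence of RIF", without a numeric margin.

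On summaries, Section 6 says "These will include the n, mean, standard deviation, CV%, median, range and geometric mean", by cohort. It adds: "For dissemination, selected descriptive statistics on evaluable participants will be used as appropriate for the data distribution". Section 7 plans individual and group concentration-time plots, a separate listing for participants outside the dose-finding population, and further outputs on request.

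Section 1 says the analysis is done "at the end of study on the completed study dataset and included in study abstracts and manuscripts". It also says that this plan complements a Primary SAP, version 2.0.

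The 63 μM·hr figure comes from the protocol's Letter of Amendment (Sections 6.5, 6.7 and 9.2). An individual AUC0-12 at or above it leads to a Protocol Team review of that child's data. For a child who permanently stops raltegravir, "evaluable PK and safety data will be used in the assessment of the dose for that cohort".

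**The concern.** The two GMs decide the dose, and each comes from at most about 12 children, yet the planned table attaches no interval to either. CV% is listed straight after the arithmetic mean and SD, so it reads as the arithmetic CV, which is not the natural measure of spread for a GM. A reader could then not tell a GM well inside the target from one whose uncertainty crosses a limit.

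Likewise, the range shows whether any child reached 63 μM·hr but not how many. One child and four children in 12 could sit behind the same maximum and the same passing GM.

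The comparability objective has no margin, so readers must judge it themselves, and they would want to see the uncertainty. Leaving the published statistics to later selection adds to the worry.

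**Working it through.** The plan states no precision, power or variability figure, so there is nothing to reproduce. The between-child log-SD (s) is assumed: 0.4 to 0.8 for AUC0-12 and 0.6 to 1.2 for C12h. From the PK SAP: n = 12, the window 14–45 μM·hr and the 75 nM target. From the Letter of Amendment: 63 μM·hr.

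**1. Width of the interval that is not named.** The 90% interval for a GM is GM/f to GM×f, with f = exp(t × s/√n) and t(0.95, 11 df) = 1.796.

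| s | f | GM AUC 16 | GM C12h 80 nM |
|---|---|---|---|
| 0.4 | 1.230 | 13.0–19.7 | – |
| 0.6 | 1.365 | 11.7–21.8 | 59–109 |
| 0.8 | 1.514 | 10.6–24.2 | 53–121 |
| 1.0 | 1.679 | – | 48–134 |
| 1.2 | 1.863 | – | 43–149 |

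Both examples pass as point estimates, and every interval shown crosses its target. But both GMs were placed next to a limit. The window's centre is √(14 × 45) = 25.1 μM·hr, with √(45/14) = 1.79-fold on each side. A GM there keeps its 90% interval inside the window up to s = ln(1.793) × √12/1.796 = 1.13, beyond the range assumed for AUC.

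**2. Can the interval be rebuilt from the planned table?** There are two routes under a log-normal model.

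- From CV%, if arithmetic: s = √ln(1 + CV²).
- From the two means: the log-normal mean equals GM × exp(s²/2), so s² ≈ 2 ln(mean/GM) × n/(n − 1).

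Example of the second route: GM 16 and mean 18.87 give 2 × ln(18.87/16) × 12/11 = 0.36, so s = 0.60 and the interval is 11.7–21.8, as in the table.

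Coverage of a nominal 90% interval over 400,000 simulated log-normal cohorts of 12:

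| s | From arithmetic CV% | From mean and GM |
|---|---|---|
| 0.4 | 88.9% | 89.9% |
| 0.6 | 87.5% | 89.7% |
| 0.8 | 85.8% | 89.5% |
| 1.0 | 83.6% | 89.2% |
| 1.2 | 81.2% | 88.8% |

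The CV route is too narrow on average but not always: its log-SD exceeds the sample log-SD in 34% of cohorts at s = 0.4, falling to 8% at s = 1.2. The two-means route loses at most about one percentage point of coverage.

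**3. Count at or above 63 μM·hr.** P(AUC ≥ 63) = 1 − Φ(ln(63/GM)/s), taken at s = 0.6.

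- GM 35: 16.4% per child. Given at least one such child, the 5th–95th percentile is 1 to 4 of 12.
- GM 25: 6.2% per child. Given at least one, it is exactly one in 69% of cohorts and at most two in 94%.

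So the maximum leaves real ambiguity about the count when the GM is in the upper part of the window, and little near its centre. An exact 95% interval would add little: 0/12 gives 0–26.5% and 1/12 gives 0.2–38.5%.

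**4. Effect on the decision.** Section 3 compares point GMs with targets that it calls approximate. Neither an interval nor a count enters that comparison, so the selected dose is the same with or without them.

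**The case for a change.** The best case for acting is that it is cheap: a short paragraph and a few table entries from data already held. For a variable C12h, a reader who has only an arithmetic CV% would rebuild an interval with true coverage near 81–84%. The better route needs both means in print, and Section 6 promises only that "selected descriptive statistics on evaluable participants will be used as appropriate for the data distribution". A count would separate one high exposure from several.

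Much of this stands. The table does not name these statistics, CV% is undefined, and publication of both means is not guaranteed. An analyst could reasonably report a geometric CV and a log-scale interval.

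It falls short of requiring a change for these reasons:

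- The list says what the summaries will include, without closing it; Section 7 allows more tables; and the published statistics are to suit the data distribution. For skewed PK data this readily admits geometric summaries.
- The 63 μM·hr value triggers a review of the individual child, so each case is examined when it arises, whatever the summary table shows.
- A single-arm interval would not measure the precision of comparability: the supplied documents contain no comparator data and no margin. For C12h its width would also depend on the half-LLOQ substitution in Section 5.1.
- The Primary SAP was not supplied, and the protocol only as amendment excerpts. Absence here does not show absence from the trial's plans.

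**Conclusion.** No change follows. Section 6 does omit an interval, an explicitly geometric CV and a threshold count, but this is missing reporting detail that analysts can fill sensibly. The dose rule can be applied as written, and adding these items would alter no dose decision, rule or error rate.

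What is lost is modest. With n, arithmetic mean and GM all published, a 90% interval can be rebuilt with 88.8% to 89.9% coverage at n = 12. The unresolved part is that the published statistics are selected later, and that the number of children at or above 63 μM·hr cannot always be read from the range.

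The figures rest on a log-normal distribution and assumed log-SDs of 0.4 to 1.2, since the documents give no variability. The finding of absence covers the supplied text only.
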